Secondary Endpoints	
 1. Clinical benefit rate (CR + PR + SD) at 1 year from treatment start with nirogacestat. Response will be assessed according to mRECIST. 2. Median progression free survival will be determined radiographically using RECIST v1.1, mRECIST and volumetrically (change in tumor volume as assessed by MRI volumetric). 3. Objective response rate at 1 year (RECIST v1.1, mRECIST and MRI volumetric); the percentage of subjects who start study treatment and achieve an objective response (CR or PR), will be calculated. 4. Time to response (RECIST v1.1, mRECIST and MRI volumetric) 5. Duration of response (RECIST v1.1, mRECIST and MRI volumetric) 6. AEs will be tabulated with frequencies and percentages for grade, severity, status, and relationship to study drug or study procedure. Assessment will be from time of consent until 30 days after the last treatment.
Exploratory Endpoint	
 • Changes from baseline in patient-reported outcomes (EQ-5D-3L)
Indication	Desmoid tumor
Sample Size	Up to 23 enrolled subjects, to achieve 20 evaluable subjects
Eligibility Criteria	Due to length, the Eligibility Criteria are only presented in one instance. Eligible subjects will be subjects \geq 18 years of age with progressive or symptomatic desmoid tumor that is at least 50% but less than 75% treatable with cryoablation. See Section 3, Subject Selection.
Dose	Nirogacestat 150 mg po BID (150 mg twice-daily) One cycle of treatment = 28 days.
Treatment and Procedural Summary	
 1. Nirogacestat 150 mg by mouth twice-daily continuously for Cycles 1 through 3. 2. Cryoablation procedure (single session) of one tumor mass between Cycles 3 and 4 of nirogacestat treatment. 3. Continued treatment with nirogacestat for Cycles 4 through 26. Treatment with nirogacestat may continue via this study protocol for up to 24 months (26 cycles of treatment), unless there is progression of disease, intolerance, start of new anticancer therapy (as defined in Sections 5.7.2 and 5.7.3), or one of the criteria in Section 3.7 (Subject Study Completion or Termination) occurs. 4. After 24 months of treatment, if clinically indicated, a subject may transition to commercial nirogacestat supply, once the subject has completed the End of Treatment (EOT) visit and is off study.

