2.2.2. Secondary Objectives

- To assess the effects of combination therapy with cryoablation plus nirogacestat on efficacy by evaluation of the clinical benefit rate (CBR) at 1 year in subjects with progressive or

symptomatic desmoid tumor. Response will be assessed according to modified RECIST criteria (mRECIST).

- To assess the effects of combination therapy with cryoablation plus nirogacestat on efficacy, by evaluation of median disease progression.
- To assess the effects of cryoablation plus nirogacestat on tumor response (as defined by objective response rate) at 1 year.
- To assess the time to response from the start of treatment with nirogacestat to the first objective tumor response.
- To assess the duration of response from time of response to time of progression.
- To assess safety and tolerability of cryoablation plus nirogacestat in subjects with progressive or symptomatic desmoid tumors.

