2.3.2. Outcome Measures for ClinicalTrials.gov Results Reporting

2.3.2.1. Primary Outcome

- **Primary Outcome Measure Title:** Clinical Benefit per RECIST v1.1

Description: Clinical benefit (CB) is defined as the number of participants assessed with a complete response (CR), partial response (PR), or stable disease (SD) within 1 year and with no evidence of loss of response nor progression within that year.

Response & progression will be assessed according to the Revised Response Evaluation Criteria in Solid Tumors (RECIST)v1.1, as follows:

RECIST v1.1:

- CR=Disappearance of all lesions
- PR= $\geq 30\%$ decrease in diameter of target lesions
- Progressive disease (PD)=20% increase in diameter of target lesion; progression of non-target lesion; or ≥ 1 new lesion(s)

For the overall outcome:

- SD=Changes not meeting above criteria
- Overall Response (OR)=CR+PR
- CB=CR+PR+SD

The outcome is a number without dispersion.

- **Time Frame:** 1 year
- **Completion of Primary Outcome:** Based on the projected accrual of 20 subjects within 24 months, the last datum for the primary objective / outcome is expected to be obtained approximately 44 months from the time the study opens to accrual.

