Description: Safety is assessed as the number of adverse events determined by the investigator to be possibly, probably, or definitely related to nirogacestat treatment (ie, drug toxicities). All related events will be collected and reported. Adverse events of Grade 3 (severe) are considered notable and potentially actionable during treatment, while adverse events Grade 1 or 2 are considered routine, with typically little or no change in treatment needed. The outcome will be reported as the number of related adverse events Grade 3 or higher is a number without dispersion.

Time Frame: 1 year

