7.3.2. Cryoablation

The risks of ablation include but are not limited to ecchymosis, edema/swelling, fever, hemorrhage, infection, delayed/non-healing wound, pneumothorax, probe site paresthesia, skin burn, and injury to off-target structures. With any procedure there is a small risk of death.

Based on CRYODESMO-01, Grade 1 and 2 toxicity occurred in 32.8% and 44.5% of subjects, Grade 3-4 toxicity occurred in 22% of subjects, and no Grade 5 toxicity was observed. The most common side effects included:¹⁶

- Pain (21.6%)
- Neural impairment (15.8%)
- Edema (15.1%)
- Musculoskeletal impairment (7.9%)
- Skin burn (5.8%)
- Increased creatinine kinase (5.8%)
- Bleeding (2.9%)
- Fever (0.7%)

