Duration of response will be summarized descriptively. If sufficient data are available the distribution will be estimated using the Kaplan-Meier method, and the Kaplan-Meier curves, medians and 95% confidence intervals of the medians will be presented.

Nominal duration of study involvement is 26 months, with last assessment after about 24 months of treatment.

10.2.2.6. **Adverse events and safety**

Adverse events will be tabulated with frequencies and percentages for grade, severity, status and relationship to study drug or study procedure. The analysis population will include all subjects who have started study treatment. Assessment for safety signals will be from time of consent until 30 days after the last treatment.

10.2.3. **Exploratory Endpoints and Analysis**

10.2.3.1. **Patient-reported outcomes (EQ-5D-3L)**

Summary measures (mean, standard deviation, median, interquartile range) of the EQ-5D-3L survey scores will be calculated for each time point during the duration of the study; scores will graphically depicted at each time point. In addition, we will calculate the difference of the scores at the baseline, time of demonstrated clinical benefit rate, and last follow-up date and report summary statistics. Nominal duration of study involvement is 26 months, with last assessment after about 24 months of treatment.

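### The safety outcome for ClinicalTrials.gov reporting (Outcome 7) counts only nirogacestat-related Grade 3+ events over 1 year, which conflicts with the combination safety objective and the planned safety analysis

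*Protocol*

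**What the plan says.** Protocol section 2.3.2 is headed "Outcome Measures for ClinicalTrials.gov Results Reporting". Of its seven outcomes, only Outcome 7 (end of section 2.3.2.2) concerns safety. It has four features:

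- **Attribution:** events judged "possibly, probably, or definitely related to nirogacestat treatment (ie, drug toxicities"). Cryoablation is not named.
- **Grade:** it first undertakes to report every related event, then states: "The outcome will be reported as the number of related adverse events Grade 3 or higher".
- **Window:** "Time Frame: 1 year".
- **Form:** a bare count of events, with no denominator and no count of subjects.

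Three other places in the Protocol address the same matter.

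- **Section 2.2.2** gives the secondary objective: "To assess safety and tolerability of cryoablation plus nirogacestat in subjects with progressive or symptomatic desmoid tumors".
- **Synopsis, secondary endpoint 6**, says: "AEs will be tabulated with frequencies and percentages for grade, severity, status, and relationship to study drug or study procedure". Its window runs from consent until 30 days after the last treatment.
- **Section 10.2.2.6** repeats this tabulation, again by "relationship to study drug or study procedure", with the same window. Its population is all subjects who started study treatment.

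Section 7.4 says that adverse events of Grade 1 and above are collected and recorded.

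**The concern.** The regimen under test is the combination. Section 4.1.3 calls the combination investigational, and section 7.3 says it is unknown whether cryoablation carries additional risks when given with nirogacestat. The outcome assigned to safety in section 2.3.2 nevertheless attributes events to the drug alone. A severe event judged related only to cryoablation would not enter it.

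The 1-year limit is not explained, although treatment may last 24 months. In the same list, duration of response has a 2-year time frame, so the posted outcomes would describe response over two years and toxicity over one.

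The grade cut also matters. In the phase 3 trial summarised in section 1.3.1, ovarian dysfunction occurred in 27 of 36 women of childbearing potential and every event was Grade 2. Comparable events here would be absent from a Grade 3+ count, even though the same paragraph promises to report all related events.

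At stake is whether the posted safety result describes the regimen that the trial studies. A reader who sees only that outcome would get a lower toxicity count than the protocol's own safety analysis would give.

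**Working it through.** The Protocol states no figure for this outcome that could be reproduced. The check compares the definitions and then sizes the difference.

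**1. Definitions side by side**

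| Feature | Outcome 7 (2.3.2.2) | Synopsis endpoint 6 and 10.2.2.6 |
|---|---|---|
| Attribution | Nirogacestat | Study drug or study procedure |
| Grade | Grade 3 or higher | All grades, tabulated by grade |
| Window | 1 year | Consent to 30 days after last treatment |
| Unit | Number of events | Frequencies and percentages |
| Population | Not stated | All who started treatment (10.2.2.6) |

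No text in the Protocol reconciles the two columns.

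**2. Time left out**

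Inputs: 26 cycles of 28 days (section 2.1.2 and synopsis), a 30-day tail (10.2.2.6), and 1 year taken as 365 days from treatment start.

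- Maximum treatment: 26 × 28 = 728 days. At 30.4375 days per month this is 23.9 months, which agrees with the stated 24 months.
- Treatment days after year 1: 728 − 365 = 363, and 363 / 728 = 49.9%.
- With the tail: 728 + 30 = 758 days; 758 − 365 = 393, and 393 / 758 = 51.8%.

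These are maxima. A subject who stops early loses less.

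**3. What excludes cryoablation events**

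Cryoablation falls between Cycles 3 and 4, at about day 3 × 28 = 84, well inside year 1. Cryoablation-only events are therefore excluded by the attribution wording and not by the time frame. Both features need correcting.

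**4. Illustrative size of the cryoablation component**

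Inputs: "Grade 3-4 toxicity occurred in 22% of subjects" (section 7.3.2, from a cited phase 2 cryoablation study) and 20 evaluable or up to 23 enrolled subjects (section 2.1.3).

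- Expected subjects: 0.22 × 20 = 4.4; 0.22 × 23 = 5.06.
- Probability of at least one: 1 − 0.78^20 = 0.993; 1 − 0.78^23 = 0.997.

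This assumes that the 22% rate applies here and that it is a per-subject rate. The text says subjects, but the quoted grade shares add to 32.8 + 44.5 + 22 = 99.3%, so they may be a distribution of events over grades. The result is also an upper figure for omissions. Under section 7.2.2 a possibly related event counts as related, and an event may be attributed to more than one cause. Any cryoablation event also judged possibly related to nirogacestat would stay in Outcome 7.

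**The case against.** The strongest reply is that Outcome 7 is a registry reporting item and not the safety analysis. Section 10.2.2.6 and synopsis endpoint 6 already cover drug- and procedure-related events for the whole treatment period plus 30 days, and the data are collected at all grades. On that view this is a wording mismatch that affects no decision rule, no data collection and no subject protection.

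Much of this stands. A reader might infer that the trial will report neither cryoablation toxicity nor second-year toxicity, or that the safety objective cannot be answered. The documents do not support either inference, because section 10.2.2.6 tabulates exactly those events. A reader might also take Outcome 7 for the trial's headline safety figure, but the Protocol does not call it that. Section 7.6 mentions a listing of serious adverse events for ClinicalTrials.gov, so some procedure-related or second-year events may appear on the registry by that route. The registry record itself was not available, so the point concerns only what section 2.3.2 prescribes.

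The reply does not remove the contradiction. Outcome 7 is the only safety outcome in section 2.3.2, it differs from the objective and the planned analysis in attribution, grade and window, and it disagrees with itself on grade. A listing of serious events is not a summary of Grade 3+ events by relationship.

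**Conclusion.** The point holds as an internal contradiction confined to the definition of Outcome 7. Followed as written, the posted safety outcome would omit events attributed only to cryoablation, and all events after year 1: up to 363 of 728 treatment days, or 393 of 758 days with the 30-day tail. It is also unclear whether related events below Grade 3 are to be reported.

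The definitional conflict and the day counts rest on the Protocol's own text, plus the convention that 1 year means 365 days from treatment start. The figure of up to about 4 to 5 subjects with Grade 3-4 cryoablation toxicity is only illustrative. It needs the cited 22% to carry over as a per-subject rate, and the number omitted reaches that level only if none of those events is judged even possibly related to nirogacestat. The finding does not depend on it.

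The efficacy analyses and the section 10.2.2.6 safety tables are unaffected. The correction is still worth making, because the posted result should match the stated objective.

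**What to change.** Reword Outcome 7 in section 2.3.2.2 to agree with section 10.2.2.6:

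- Count events related to nirogacestat, to cryoablation, or to either, and show the three separately.
- Use all subjects who started study treatment as the population.
- Run the window from consent to 30 days after last treatment. Starting it at first dose would create a new mismatch with 10.2.2.6.
- Give the number and percentage of subjects with at least one event, as well as the number of events.
- Settle the grade wording. Either report all related events by grade, or keep Grade 3 or higher and delete the promise to report all related events.

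The registry entry should then be checked against the revised text. The cost is a wording amendment with no new data collection. The only downside is that the posted toxicity figure may look less favourable.

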3. SUBJECT SELECTION

3.1. Eligibility Criteria and Participant Eligibility Checklist

Inclusion and Exclusion Criteria are provided on the Eligibility Checklist which may be extracted from this document for use in screening potential subjects.

The Participant Eligibility Checklist must be completed in its entirety for each subject prior to registration. The completed, signed, and dated checklist is retained in the subject's record. Screening results will be collectively documented on the Study Participant Log.

Pursuant to Stanford Cancer Institute SOP "Confirmation of Participant Eligibility in Clinical Trials," the treating Physician (investigator), the Study Coordinator, and an Independent Reviewer will verify that the subject's eligibility is accurate, complete, and legible in source

records. A description of the eligibility verification process should be included in EPIC or other Electronic Medical Record progress note.

Participant Eligibility Checklist

I. Protocol Information

Protocol Title:	Phase 2 Study of Cryoablation and Nirogacestat for Desmoid Tumor
Study Identifiers:	eProtocol: IRB-67799 Oncore: SARCOMA0061 SpringWorks Therapeutics program / protocol number: NIR-DT-602
Principal Investigator:	[name].

II. Subject Information

Subject Initials / Unique ID:	/
Gender	 Male  Female

III. Eligibility Criteria

3.1.1. Inclusion Criteria

Prospective Participant Must Meet ALL these Inclusion Criteria to be Eligible	Yes	No	Supporting Documentation *

1. Histologically-confirmed diagnosis of desmoid tumor (DT) that is progressing (by RECIST criteria over the past 12 months) or symptomatic (as defined by change in pain regimen or impairment of activities of daily living (ADLs), or at investigator discretion).
 
Note: Must have diagnosis of desmoid tumor on pathology report.
			
Pathology Date: _____
 
Progress notes: _____

Prospective Participant Must Meet ALL these Inclusion Criteria to be Eligible	Yes	No	Supporting Documentation *

2. Desmoid tumor is 50 to <75% cryoablatable.
 
Tumors that are 50 to <75% (volume) ablatable in a single session which may be characterized by:
 
 a. Proximity (< 1 cm) to critical structures, such as nerves, vessels, bowel, or skin, at risk of injury during ablation, despite hydrodissection, and/or b. Large size (> 100 mL), and/or c. Complex shape, such that parts of the tumor cannot be reached from a single approach or subject position, and/or d. Thin, infiltrative components, where ablation of that portion would damage more normal anatomy than tumor (e.g., tumor extending along a fascial plane between muscles, such that ablation would damage more muscle than tumor volume) 			

3. If participant is currently being treated with any therapy for the treatment of DT, this must be completed at least 28 days (or 5 half-lives, whichever is shorter) prior to first dose of study treatment. All toxicities from prior therapy must be resolved to ≤ Grade 1 or clinical baseline.
			

4. Participants who are receiving chronic nonsteroidal anti-inflammatory drugs (NSAIDs) as treatment for conditions other than DT must be on a stable dose for at least 28 days prior to first dose of study treatment.
			

5. Age ≥ 18 years.
			

6. Participant has an Eastern Cooperative Oncology Group (ECOG) performance status ≤ 2 at screening.
			ECOG: _____ Date of ECOG: _____

Prospective Participant Must Meet ALL these Inclusion Criteria to be Eligible	Yes	No	Supporting Documentation *

7. Participant has adequate organ and bone marrow function as defined by the following screening laboratory values:
 
a. Absolute neutrophil count \geq 1500 cells/μL;
 
b. Platelets \geq 100,000μL;
 
c. Hemoglobin \geq 9 g/dL;
 
d. Total bilirubin \leq 1.5 \times upper limit of normal (ULN) (isolated bilirubin $>$ 1.5 \times ULN is acceptable if bilirubin is fractionated and direct bilirubin $<$ 35%);
 
e. Aspartate aminotransferase (AST) (serum glutamic oxaloacetic transaminase)/alanine aminotransferase (ALT) (serum glutamic pyruvate transaminase) \leq 2 \times ULN; and
 
f. Serum creatinine \leq 1.5 \times ULN or if creatinine $>$ 1.5 \times ULN then calculated creatinine clearance must be \geq 60 mL/min (using the Cockcroft-Gault formula)
	      	   	
ANC: _____
 
Platelets: _____
 
Hb: _____
 
Total bilirubin: _____
 
AST: _____
 
ALT: _____
 
Creatinine: _____

8. Women of childbearing potential must have a negative serum pregnancy test at screening.
			
Serum pregnancy test: Date: _____ Result: _____

9. Participant can swallow tablets.			
10. Participant able to have MRI.			

11. Ability to understand and the willingness to personally sign the written IRB-approved informed consent document.
 
Note that this study does not allow the use of a legally-authorized representative.
			

Prospective Participant Must Meet ALL these Inclusion Criteria to be Eligible	Yes	No	Supporting Documentation *

12. Contraceptive use by men or women should be consistent with the standard that will be used at Stanford regarding the methods of contraception for those participating in clinical studies.
 
a. Male participants: Male participants are eligible to participate if they agree to the following during the treatment period and for at least 1 week after the last dose of study treatment:
 
 Refrain from donating or preserving sperm for at least 90 days after the last dose of active study treatment; 
PLUS either:
 
 Be abstinent from sexual intercourse as their preferred and usual lifestyle (abstinent on a long-term and persistent basis) and agree to remain abstinent; 
OR
 
 Must agree to use a male condom when having sexual intercourse with women of childbearing potential (WOCBP). An additional form of contraception as described in Appendix H should also be used by the female partner, if she is of childbearing potential. 
Postmenopausal state (not of childbearing potential) is defined as no menses for 12 months without an alternative medical cause.
 
b. Female participants: A female participant is eligible to participate if she is not pregnant or breastfeeding, and at least one of the following conditions applies:
 
 Is not of childbearing potential (not WOCBP), OR Is of childbearing potential but is abstinent or using 1 highly effective contraceptive method, as described in Appendix H during the treatment period and for at least 1 week after the last dose of active study treatment. 
A second method of contraception is required if the participant is using hormonal contraception, as coadministration with nirogacestat may alter the plasma concentrations of hormonal contraceptives resulting in reduced efficacy. Additionally, the participant agrees not to harvest or donate eggs (ova, oocytes) for the purpose of reproduction during the treatment period and for at least 6 months after the last dose of active study treatment. The investigator should evaluate the effectiveness of the contraceptive method in relationship to the first dose of study treatment.
 
 The investigator is responsible for review of medical history, menstrual history, and recent sexual activity to decrease the risk for inclusion of a woman with an early undetected pregnancy. 			
